**Table 2. Study Schedule of Procedures**

Procedure	Screening	Visit 1 (Consent)	Visit 2	Visit 3	Visit 4
Review Eligibility criteria	X	X			
Consent for research participation		X			
Documentation-medical history, medications, &		X	X	X	X

clinical data					
Physical Examination			X	X	X
PTS Assessment: modified Villalta, DASH			X	X	X
Blood draw- D-dimer, thrombin generation, TFPI, plasma free DNA (MCW Only)			X	X	X

## 6. Laboratory Procedures

### 6.1 Plasma preparation

Tube 1 of citrated blood will be used to prepare PRP and tubes 2 and 3 of citrated blood will be used to prepare PPP. Tube 1 will be centrifuged at 130 g at room temperature for 10 minutes within 30 minutes of blood collection. After centrifugation, the PRP will be pipetted off without disturbance of the white blood cell layer (buffy coat). 200 ul of PRP will be used to assess the platelet count via a Coulter counter. Approximately half of the PRP will be placed into centrifuge tubes for preparation of PPP by centrifugation at 2000g for an additional 10 minutes. Tubes 2 and 3 will undergo centrifugation at 2000g for 10 minutes and centrifugation at 14,000 g for 5 minutes at room temperature. PPP will be obtained from the upper half volume of plasma supernatant. PPP will be used to adjust the platelet count of the PRP to 150,000/uL. The unused PPP will be frozen to allow batched processing of thrombin generation, D-dimer, plasma free DNA and TFPI testing.

### 6.2 Thrombin Generation

Thrombin generation will be measured through a calibrated automated thrombogram system (CAT, Thrombinoscope bv, Maastricht, The Netherlands) with and without tissue factor activation using both PRP and PPP. Each well of the 96-well plate will contain 20 ul of reagent (PPP-Reagent or PRP-Reagent), 20 ul of thrombin calibrator, and 80 ul of plasma. Plasma samples will be measured in duplicate.

### 6.3 D-Dimer

The Stago Asserachrom® D-Di ELISA assay will be used to determine D-dimer levels. The Asserachrome ELISA has similar sensitivity and specificity as other D-dimer assays in clinical use. Batched laboratory testing will prevent clinical decisions from being altered by the D-dimer results.

## 6.4 TFPI Assay

Levels of platelet TFPI (TFPI $\alpha$ ), plasma total TFPI and TFPI $\alpha$  will be assessed through TFPI AlphaLISA assays. AlphaLISAs are a washless, bead based assay system. When the two beads are brought into close proximity by antigen binding, a singlet oxygen is released from the donor bead to the acceptor bead, resulting in light emission. Two AlphaLISAs are established in the lab to measure TFPI, one for total TFPI (full length TFPI $\alpha$ , truncated TFPI $\alpha$ , and TFPI $\beta$ ) and one specifically for TFPI $\alpha$ . Both assays use a common acceptor bead to which mouse anti-human TFPI antibody (directed toward the second Kunitz domain) is conjugated. The total TFPI AlphaLISA uses biotinylated 2H8 (directed toward the first Kunitz domain) to detect all forms of TFPI, while the TFPI $\alpha$  AlphaLISA uses a biotinylated anti-K3 antibody to detect only TFPI $\alpha$ . A streptavidin-conjugated donor bead is added to bind these antibodies. Each well of the 96-well plate will contain 5ul of plasma and 20 ul mixture of anti-K2 conjugated acceptor bead and either the biotinylated 2H8 to measure total TFPI or biotinylated anti-K3 to detect TFPI $\alpha$ . Plasma samples will be measured in duplicate.

## 6.5 Plasma Free DNA

Levels of plasma free DNA will be assessed using the Quant-iT PicoGreen dsDNA kit and the Sytox Green fluorescent dye. The Victor microplate reader will be used to determine the fluorescence omitted from the samples. The DNA concentration will be determined through comparison to a standard curve.

## 7. Subject Remuneration

For their time and efforts in study activities, research subjects will receive \$25 for each of the following patient visits:

- Study visit 2, 1 month after catheter removal
- Study visit 3, 3 months after catheter removal
- Study visit 4, 6 month after catheter removal

A total of \$75 will be paid to subjects completing all study visits to cover travel to the research site, parking, and time of the visits. The subject will be paid \$25 for each completed study visit whether they withdraw, the investigator withdraws them or they complete all study activities. Payment will occur when they are no longer an active participant in the study. Remuneration for study visits will only take place at the BCW site.

### 7.1 Potential benefit to subjects

Our protocol will treat participants with anticoagulation for 1 month after catheter removal. There are no definite direct benefits to subject participation. Because the

duration of anticoagulation varies in clinical practice, treatment with one month of anticoagulation could have lower risk of hemorrhage in comparison to 3 or 6 months of anticoagulation. Additionally, the cost and discomfort associated with use of injected anticoagulant could be lower. The study may also benefit others with CRT if the study is able to identify biomarkers that will predict thrombosis to allow a tailored approach to treatment of CRT.

## 8. Human Subjects Protection

- 8.1 Informed Consent:** Subjects are required to sign an informed consent prior to enrollment, and before undergoing any study procedures or assessments. When substantial modifications are made to the informed consent, the IRB may require that all subjects currently enrolled in the study will be re-consented.

Subjects will be provided with a copy of the signed informed consent form used in the study, procedures, and assessments. Subjects will also be provided with the contact telephone numbers of the investigator and qualified personnel who can assist with their questions and concerns.

### 8.2 Protected Health Information

Protected health information that will be collected as part of this study includes name, date of birth, date of catheter placement, date of thrombosis diagnosis, date of bleeding event, and date of thrombosis recurrence. This information will be stored for 10 years beyond the completion of the study. After blood is used for study testing it will be discarded.

### 8.3 Confidentiality

Loss of confidentiality is always a potential risk when collecting protected health information. Research records will remain confidential. Subject's records will be available to the study staff and to each site's IRB and for audit purposes. Only authorized personnel will have access to the protected health information and research records. The investigators, clinical research nurses, and TRU nurses will have access to the patient identifying code. In order that confidentiality can be maintained, the PI/study staff will keep records in locked cabinets/room and results of tests will be coded to prevent association with volunteers' names. All electronic data will be entered into a secured, website data management system, REDCap, that requires training and is password protected. Identifying information will not be included on laboratory samples,

faxes, or correspondence. Laboratory samples and printed surveys will only have participant number and not identifying information.

All study team members are trained in HIPAA privacy regulations and other applicable site privacy policies. No information will be released, nor will participation in the research be acknowledged, to any party except where compulsory according to law or institutional policy. The results of the research study may be published, but volunteers' names or identities will not be revealed.

## 9. Adverse Event Monitoring

### 9.1 Definitions

**Adverse Event (AE)** – Any untoward or unfavorable medical occurrence in a human subject related to bleeding or thrombosis, including any abnormal sign (for example, abnormal physical exam or laboratory finding), symptom, or disease, temporally associated with the subject's participation in research, whether or not considered related to the subject's participation in research.

**Serious Adverse Event (SAE)** – Any adverse event temporally associated with the subject's participation in research and related to bleeding or thrombosis that meets any of the following criteria:

- Results in death;
- Is life-threatening (places subject at immediate risk of death from the event as it occurs);
- Requires inpatient hospitalization or prolongation of existing hospitalization;
- Results in a persistent significant/incapacity;
- Results in a congenital anomaly/birth defect; or
- Any other adverse event that, based upon appropriate medical judgment, may jeopardize the subject's health and may require medical or surgical intervention to prevent on the other outcomes listed in this definition

Note that seriousness and severity are separate concepts. The term "severe" refers to the intensity of a specific event; a severe event may be of minor medical significance (e.g., a severe leg cramp). The term "serious" is based on an outcome or action criteria that are usually associated with events that pose a threat to the patient's life or functioning. An event that is mild in severity is serious if it leads to one of the outcomes defined above.

Grade 4 and 5 events will always be considered Serious Adverse Events. Many Grade 3 and some Grade 1 and 2 events may meet the definition of a Serious Adverse Event.

Unexpected Adverse Event- Any adverse event occurring in one or more subjects in a research protocol, the nature, the severity, or frequency of which is not consistent with either:

- The known or foreseeable risk of adverse events associated with the procedures involved in the research that are described in;
  - the protocol related documents or the current IRB-approved informed consent document and;
  - other relevant sources of information, such as a product labeling or package insert or;
- The expected natural progression of any underlying disease, disorder, or condition of the subject(s) experiencing the adverse event and the subject's predisposing risk factor profile for the adverse event.

Unanticipated problem involving risks to subjects or others (UP) - Any incident, experience or outcome that meets all the following criteria:

- Unexpected (in terms of nature, severity, or frequency) given:
  - The research procedures that are described in the protocol related-documents, such the IRB-approved research protocol and the informed consent form document and,
  - The characteristics of the subject population being studied;
- Related or possibly related to the subject participation in research; and
- Suggests that the research places subjects or others at a greater risk of harm (including physical, psychological, economic, or social harm) related to the research than was previously known or recognized.

Grading of Adverse Events – Events will be graded by using the Common Terminology Criteria for Adverse Events (CTCAE) Criteria version 4.0.

Attribution – the determination and documentation of whether an adverse event is related to a medical procedure.

Attribution Categories:

1. Not Related –Event clearly related to other factors (e.g., clinical state, other therapies; concomitant drugs)

2. Possible Related – Sequence of event is compatible with study drug, device, or procedure, but could have been produced by other factors
3. Probably Related - Sequence of event is compatible with study drug, or procedure and cannot be explained by other factors without much doubt
4. Definitely Related - Sequence of event is compatible with study drug, or procedure and beyond doubt cannot be explained by other factors

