## **9.4 Timeline for Reporting of Adverse events, Serious Adverse Events, Unexpected Adverse Events and Unanticipated Problems**

All serious adverse events, all unexpected adverse events, and all unanticipated problems will be reported to the IRB and DSMC as per standard operating procedure by phone, email or SAE form regardless of attribution.

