**Less Likely:**

**Blood Sampling:** Venipuncture can cause, bruising, fainting or local infection at the needle site.

**Survey:** Filling out the surveys could cause stress or anxiety to the participant

**Physical Exam:** Examining the chest cause participant embarrassment

**Anticoagulation:** Use of anticoagulation is known to cause an increased risk of bleeding that can occur at the injection site or systemically. Use of anticoagulation is known to cause an increased risk of bleeding that can occur at the injection site or systemically. Participants will have had anticoagulation for 0-6 months prior to catheter removal and one month after catheter removal. Usual care would include anticoagulation between 1-3 months after catheter removal. With a shortened course of anticoagulation, an increased risk of thrombosis or post-thrombotic syndrome could occur.

Potential side effects of enoxaparin include fever, nausea, diarrhea, fluid retention, elevated LFTs, decreased platelets, decreased RBCs, local irritation, hematoma and redness.

A potential side effect of all direct oral anticoagulant treatment includes bleeding. Edoxaban also reported a rash, abnormal liver function tests, and anemia. Dabigatran is also associated with gastritis-like symptoms in 15% of patients.

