**Rare:**

**Blood Sampling:** In rare circumstances venipuncture can cause blood clots, peripheral nerve injury or an arterial puncture.

**Anticoagulation:** The anticoagulation medication prescribed from the treating provider as planned treatment for catheter-related thrombosis can rarely cause bleeding requiring hospital admission, transfusion, or death.

**Breach of confidentiality:** personal health information will be collected and rarely a breach of confidentiality may lead to disclosure of that information.

In addition to the above possible risks, there is always the risk of developing previously unknown side effects.

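### The bleeding-or-thrombosis limit in the AE and SAE definitions omits several blood-draw harms that 9.7 names and leaves deaths of undetermined cause without a clear reporting rule

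*Combined protocol and SAP*

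**What the plan says.** Section 9.1 defines an AE as "Any untoward or unfavorable medical occurrence in a human subject related to bleeding or thrombosis, including any abnormal sign". Relation to the study is not required: the event counts "whether or not considered related to the subject's participation in research". The SAE definition carries the same limit, since the event must be temporally associated with "participation in research and related to bleeding or thrombosis that meets any of the following criteria", and death is one of the criteria that follow. Further down, 9.1 states without repeating the limit: "Grade 4 and 5 events will always be considered Serious Adverse Events". An unexpected adverse event begins as "Any adverse event occurring in one or more subjects in a research protocol", so it is a subset of AEs.

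Unanticipated problems, also in 9.1, are not confined to bleeding or thrombosis. They must be unexpected, at least possibly related to participation, and suggestive of more risk than was known.

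Section 9.4 sends SAEs, unexpected AEs and unanticipated problems onward; these "will be reported to the IRB and DSMC as per standard operating procedure by phone, email or SAE form regardless of attribution". Section 9.5 adds IRB notice of unanticipated deaths after participation ends, if they may reasonably be study-related.

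On the blood draws, 9.7 lists pain and discomfort as likely. Under less likely it says: "Venipuncture can cause, bruising, fainting or local infection at the needle site". Under rare: "In rare circumstances venipuncture can cause blood clots, peripheral nerve injury or an arterial puncture".

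**The concern.** Limiting safety reporting to the outcomes of interest is understandable in a cohort under active cancer treatment. The difficulty is that the limit governs two things it should not.

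First, the venipunctures at Visits 2 to 4 are done for research. Harms they cause are the study's own responsibility, and the plan names several that its definitions give no reason to record.

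Second, a death can be placed inside or outside the SAE definition only once its link to bleeding or thrombosis is known. In a sudden or unwitnessed death that link may never be established, and the plan does not say who decides or how an undetermined cause is handled. This matters because 9.7 itself warns that the shorter course could increase thrombosis, and Section 1 cites pulmonary emboli in 15% of patients with symptomatic catheter-related thrombosis. A death in which pulmonary embolism (PE) cannot be excluded is something the DSMC needs to see.

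**Working it through.** No figure in the plan needs reproducing here. The check sets the definitions, the reporting routes and the named risks side by side.

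**1. Which activities inherit the limit.** Site monitor review (9.2), staff collection and PI review (9.3) and the biannual DSMC report (10.3) are all framed in terms of adverse events or SAEs. The contents listed in 10.3 are patients entered, patients treated, an AE summary and an SAE list; no separate count of deaths is listed. Mortality is not an endpoint in 11.1, and the dates listed in 8.2 include bleeding and recurrence but not death.

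**2. Blood-draw risks in 9.7 sorted against the AE definition.**

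| Risk named in 9.7 | Bleeding or thrombosis? | AE under 9.1? |
|---|---|---|
| Pain, discomfort | No | No |
| Fainting | No | No |
| Local infection | No | No |
| Peripheral nerve injury | No | No |
| Blood clots | Yes | Yes |
| Bruising | Arguably, as bleeding | Arguably |
| Arterial puncture | Arguably, as bleeding | Arguably |

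The attribution step in 9.1 asks whether an adverse event is related to a procedure. The first four rows never become adverse events, so that question is never put.

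**3. Whether the unanticipated-problem route recovers them.** It requires the event to be unexpected given the procedures described in the protocol and consent form. A risk already listed in 9.7 is not unexpected in nature. Only unusual severity or frequency could bring it in, and it must also suggest greater risk than was known. An ordinary faint or a single local infection would not meet this.

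**4. A death of undetermined cause, route by route.**
- *SAE definition:* not met unless a link to bleeding or thrombosis is accepted.
- *Grade 4 and 5 sentence:* take Grade 5 to be death, as in the CTCAE scale that 9.1 adopts. Read alone, the sentence makes every death an SAE. Read as grading only events already classed as AEs, it adds nothing. The text supports either reading.
- *Unanticipated problem:* all three criteria must hold, and expectedness is judged partly on the study population. A death during active cancer can readily be called expected.
- *Section 9.5:* applies only after participation ends, only to unanticipated deaths with a reasonable link to the study, and names the IRB and regulators but not the DSMC.

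Some deaths would be reported by these routes. None of them ensures that all are.

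**5. Size of the exposure.** Section 4.2 plans 36 patients at the Milwaukee site. Section 5.6 and Table 2 give one research draw at each of Visits 2, 3 and 4, at that site only.

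36 patients × 3 draws = 108 draws at most.

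The realised number will be lower. Section 4.2 allows 10% drop-out, and 3.5 omits laboratory assessments when anticoagulation runs beyond one month after catheter removal. If 10% of the Milwaukee patients gave no samples, the figure would be 108 × 0.9 ≈ 97.

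**The case against.** The strongest defence is that this is a 56-patient pilot in people with active cancer, using anticoagulants chosen and prescribed by the treating physician. Full AE collection would mostly record chemotherapy toxicity and disease progression. That stands, and the narrow definition should remain for such events. It does not reach harms from the study's own procedures, and it is no reason to leave deaths unclear.

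Three stronger readings are tempting, and the documents do not support them.

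- *That unexplained deaths and blood-draw injuries escape AE and SAE reporting altogether.* Clots fall inside the definition, and bruising and arterial puncture arguably do. The Grade 4 and 5 sentence, the unanticipated-problem rule and 9.5 each leave a route for some deaths. Sites also follow institutional procedures, and the DSMC works to a monitoring plan; neither is reproduced here. It therefore cannot be said that deaths would not reach the DSMC.
- *That 9.1 contradicts 9.4.* Attribution is a defined term in 9.1: it concerns relation to a study drug, device or procedure, not cause of death. Reporting bleeding and thrombotic events whatever their attribution is consistent with the definitions.
- *That the AE wording biases the recurrence count or could decide the interim boundary of 8 in 20.* Recurrence is a separate secondary endpoint (11.1.3), analysed as a proportion (11.2), with its date collected (8.2). Section 10.4 places the boundary under an adverse-event heading, but nothing says the count is taken from the AE list. A fatal embolism put down to cancer would be missed under any AE definition; that is a question of endpoint ascertainment.

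**Conclusion.** The point holds as a gap and an internal inconsistency in 9.1. Four kinds of blood-draw harm named in 9.7 fall outside the AE and SAE definitions and would normally fall outside the unanticipated-problem rule. For deaths of undetermined cause, the SAE definition and the Grade 4 and 5 sentence point in different directions, and the remaining routes are partial.

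The consequence is incomplete safety oversight; no bias in an efficacy or recurrence estimate has been shown. The 108 draws bound the exposure and say nothing about how often harm occurs. The number of deaths affected cannot be estimated from the documents. The conclusion assumes that staff apply 9.1 as written and that the unseen procedures and monitoring plan do not already require all deaths and procedure injuries to be reported. It is a worthwhile, inexpensive correction and not a threat to the study's main conclusions.

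**What to change.** Keep the present definition for routine cancer and chemotherapy events, and add two classes to 9.1:

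- (a) Every death from consent to Visit 4, whatever the cause, reported as an SAE to the IRB and DSMC, with a field recording thrombosis, bleeding, neither, or cannot be excluded. This reconciles the SAE definition with the Grade 4 and 5 sentence.
- (b) Any event at least possibly related to a research procedure, meaning the blood draws and the study examinations.

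In the interim report to the DSMC, list deaths in which PE cannot be excluded on a separate line beside the recurrence count.

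The cost is one paragraph in 9.1, one REDCap field and one line in the interim report. The downside is that a few deaths from cancer progression and some minor procedure events will be reported that might not be under the present wording. With 56 patients that burden is small.

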## **9.2 Site Monitor Physician**

A site monitor physician will be identified at each site. [name] is the site monitor physician at MCW. [name] will be the site monitor physician at OSU.

The site monitor physician will:

- 1) Assess all adverse events and the frequency of adverse events
- 2) Report directly to the IRB in the event of a serious adverse event

## **9.3 Study Staff**

Information on all adverse events, whether reported by the subject, directly observed, or detected by physical examination, laboratory test or other means, will be collected, recorded, followed, and reported as described in the following sections. If follow-up or clinical intervention is required, the treating provider will be informed and will provide treatment or follow-up as needed.

The PI will monitor and review adverse events monthly or more often as needed.

